9.1 Study design

This is a Post Authorization Safety Study according to the EU Volume 9a of the Rules Governing Medicinal Products in the European Union and is planned as a prospective, multicenter, multi-national disease registry for patients diagnosed with myelofibrosis. The study is planned to recruit patients diagnosed with MF exposed and non-exposed to ruxolitinib with the objective of enrolling at least 300 patients exposed to ruxolitinib within 2 years. It is expected that about 150 patients not exposed to ruxolitinib will be recruited during the enrolment period.

Participating sites will be identified in collaboration with European Leukemia Net (ELN, an academic network of excellence dedicated to improve the treatment of patients with hematologic malignancies). To allow the recruitment of 300 patients, it is expected that 100 sites will be participating in this MF disease registry.

9.1.1 Visit schedule and assessments

This study is non-interventional or observational in nature and does not impose a therapy protocol, diagnostic/therapeutic interventions or a visit schedule. Available data from routine clinical management of the patients will be collected at patients' visits to their site. To maintain adequate data collection, the sites will be encouraged to provide any updated patient data at 3-monthly intervals.

9.1.2 Discussion of study design and feasibility

To date, no large prospective observational studies have been reported that provide insight into current treatment patterns or detailed information on disease associated conditions and outcomes.

The chosen design will allow collection of data on all patients with a confirmed diagnosis of MF, irrespective of treatment modalities employed, disease severity, age, concurrent conditions or other factors that are typically controlled in interventional settings by inclusion-or exclusion criteria. Data on drug exposure including ruxolitinib, the emergence and management of events of special interest, the use of combination drug therapies, and the outcome of pregnancies will be made available. In addition, the non-interventional study logistics allow the collection and transmission of SAE and ADR data collected for patients exposed to ruxolitinib.

Ruxolitinib as an innovative treatment is intended for the long term treatment of MF. The design and logistics of the non-interventional study will allow a follow-up of "real-world" patients for 3 to 5 years. This is significantly longer than exposure experience from ruxolitinib clinical studies in MF patients. Furthermore, the disease registry will allow the continued follow-up of patients independent of exposure to certain drugs. The study will collect data from several European countries. This may balance for local treatment patterns.

There are several limitations to the study: a direct comparison or hypothesis testing between patients exposed to ruxolitinib and those who are not will not be possible due to confounding factors; i.e., patients with few manifestations of MF are expected to be managed differently from those with a more serious manifestations such as massive splenomegaly and pronounced disease symptoms. Still, data received on non-exposed patients will provide valuable context information that support the interpretation of observations made. Potential or identified risks related to ruxolitinib drug treatment have been characterized and quantified in (interventional) phase III clinical studies and therefore represent an important reference. It will therefore be possible to review solicited safety observations from this non-interventional study in the context of the safety profile of ruxolitinib established from MF clinical studies.

This Post Authorization Safety Study is aiming to collect comprehensive data on the evolution and management of the condition rather than on isolated parameters. The primary objective is to collect *long-term* safety data for ruxolitinib exposed patients. Therefore, for selection of participating sites several aspects were reviewed:

Novartis	Confidential	Page 18
Non-Interventional Study Ame	nded Protocol v01 (Clean)	Study No. CINC424AIC01T

Firstly, participating centers have to be qualified for the treatment and management of patients with hematologic malignancies and have the infrastructure for adequate data management according to GCP, including back-up of trained personnel. Secondly, to reduce missing data or loss to follow-up centers should offer, ideally within the same institution, medical services from other disciplines that are required for the management of MF complications or MF treatment escalation.

Major academic centers organized within the ELN were therefore contacted and requested to provide an estimate of the number of patients diagnosed with MF. Data from ELN centers indicated 10-20 patients with MF are currently managed per site, whereas it is expected by the experts that eligible mid-size sites currently manage 3-5 patients. It was assumed that 85% of MF patients at a site will provide informed consent for the data collection in the disease registry.

Based on above information and assumptions, and considering the participation of 15 large sites the recruitment of 300 MF patients exposed to ruxolitinib in the registry within 2 years, it is estimated that 100 centers will be required to reach the recruitment target. A total of 100 suitable centers were identified in collaboration with the ELN in EU countries.

The recruitment of patients will be monitored on a continuous basis by Novartis. If the recruitment rate falls below projections, Novartis will make any effort to identify and qualify additional sites. The identification of additional sites will be performed with involvement of the ELN, for which the ERNEST registry will provide information on potential candidates.

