9.3.2 Baseline disease characteristics and demographics

Unless otherwise stated, *baseline* is defined as the first observation at the time the patient is included in the registry. The following information will be collected at baseline:

- 1. Patient age, gender and race
- 2. MF diagnosis (major and minor criteria which qualified the patient for diagnosis of MF)
- 3. Date of first diagnosis of MF
- 4. MF current risk group (DIPSS risk category for patients previously diagnosed and IPSS risk category for newly-diagnosed)
- 5. JAK2V617F mutation status
- 6. Spleen Length
- 7. Constitutional Symptoms
- 8. Body weight
- 9. Prior transfusional history (PRBC's and platelets)
- 10. Date and results of bone-marrow biopsies (including fibrosis score and staining methodology)
- 11. Prior treatments of MF, including dose, dates and duration (whichever data are available), including interventions such as splenectomy or irradiation therapy
- 12. Co-morbidities, including organ impairments and previous infections
- 13. Prior history of malignancies with date of first diagnosis, pathology, treatments and current state

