9.7.4 Primary objective

The primary objective of this non-interventional study is to document long-term safety in patients with myelofibrosis prescribed ruxolitinib according to the prescribing information.

Data will be summarized descriptively and separately for patients exposed and non-exposed to ruxolitinib.

The incidence of on-treatment Adverse Drug Reactions and SAEs will be summarized by system organ class and preferred term using the MedDRA dictionary. Similar summaries will also be produced for treatment-related SAEs. These listings will cover both events that occur during the on-treatment and post-treatment period however, events that occur during the post- treatment period will be flagged. All ADR and SAE data will be analyzed according to the specifications of the ruxolitinib risk management plan.

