Section 9: Study size and power	Yes	No	N/A	Protocol section(s)
9.1 Is sample size and/or statistical power calculated?	\bowtie			9.7.7
Comments:				

No

Section 10: Analysis plan	Yes	No	N/A	Protocol section(s)
10.1 Does the plan include measurement of excess risks?		\boxtimes		
10.2 Is the choice of statistical techniques described?		\boxtimes		
10.3 Are descriptive analyses included?	\boxtimes			9.7
10.4 Are stratified analyses included?		\boxtimes		
10.5 Does the plan describe methods for adjusting for confounding?		\boxtimes		
10.6 Does the plan describe methods addressing effect modification?			\boxtimes	

Comments:

No

Section 11: Data management and quality control	Yes	No	N/A	Protocol section(s)
11.1 Is information provided on the management of missing data?		\boxtimes		
11.2 Does the protocol provide information on data storage? (e.g. software and IT environment, database maintenance and anti-fraud protection, archiving)	\boxtimes			9.6.2/9.63
11.3 Are methods of quality assurance described?	\square			9.8
11.4 Does the protocol describe possible quality issues related to the data source(s)?		\boxtimes		
11.5 Is there a system in place for independent review of study results?		\boxtimes		
Commente				

Comments:

No

Section 12: Limitations	Yes	No	N/A	Protocol section(s)
12.1 Does the protocol discuss:				
12.1.1 Selection biases?		\square		

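### The non-exposed cohort is offered as context and disease severity is named as the confounder, yet summaries are planned by exposure only, so crude death and special-interest event figures could mislead

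*Protocol*

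**What the plan says.** Section 9.1.2 of the protocol rules out a formal contrast: "a direct comparison or hypothesis testing between patients exposed to ruxolitinib and those who are not will not be possible due to confounding factors". It names the mechanism: "patients with few manifestations of MF are expected to be managed differently from those with a more serious manifestations such as massive splenomegaly". It then gives the second cohort a purpose: "data received on non-exposed patients will provide valuable context information that support the interpretation of observations made". The same section names the phase III studies as another reference.

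The presentation is set in 9.7.4, in the same words as in 9.7.2: "Data will be summarized descriptively and separately for patients exposed and non-exposed to ruxolitinib". No other grouping is given there, and 9.7.5 only restates the secondary objectives.

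Section 9.3.2 lists at baseline "MF current risk group (DIPSS risk category for patients previously diagnosed and IPSS risk category for newly-diagnosed", together with spleen length and constitutional symptoms.

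In Annex 2 the answer is No to item "10.4 Are stratified analyses included", to item "10.5 Does the plan describe methods for adjusting for confounding", and to item 7.1 on known confounders. Section 9.9, on limitations, is marked not applicable, although 9.1.2 says that there are several.

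Under 11.1, events of special interest (bleeding, serious or opportunistic infections, secondary malignancies including AML, deaths) are collected in all enrolled patients. ADRs and SAEs (11.2) and the Safety set (9.7.1) concern exposed patients.

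**The concern.** Using one cohort to interpret the other is an informal comparison, even when no test is made. If the two cohorts differ in severity, as 9.1.2 expects, a crude event proportion in the non-exposed patients is not the background that exposed patients would have had. A reader could take a gap in deaths, infections or AML as a signal about the drug, or could miss one that severity offsets. The protocol lists the variables needed to show this at baseline, but the stated presentation does not use them beyond the general baseline summary. About 150 non-exposed patients are to be recruited for context, and that context is weak if severity is not shown alongside the outcomes.

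**Working it through.** **The plan's own figure.** No figure in the protocol concerns the exposed versus non-exposed contrast. The detection statement in 9.7.7 concerns exposed patients only, and it reproduces: 1 − 0.99^300 = 0.951, against the stated 95%.

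**Inputs from the protocol.** Median survival by IPSS group (section 7): 135, 95, 48 and 27 months. Planned follow-up: 3 to 5 years (9.1.2). Cohorts: 300 exposed and about 150 non-exposed (9.5, 9.7.7).

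**Assumptions.** Survival is exponential within each risk group. There is no drug effect. The risk mixes are mine, because the documents give none. They put more high-risk patients in the exposed cohort, a direction that 9.1.2 implies but does not state.

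**Step 1. Death risk by group:** 1 − 2^(−T/median).

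| | Low | Int-1 | Int-2 | High |
|---|---|---|---|---|
| T = 36 months | 0.169 | 0.231 | 0.405 | 0.603 |
| T = 60 months | 0.265 | 0.355 | 0.580 | 0.786 |

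**Step 2. Crude risk in each cohort:** the sum of share × risk. Mixes are Low/Int-1/Int-2/High in percent. For the mild case at 3 years:
- exposed: 0.15 × 0.169 + 0.30 × 0.231 + 0.35 × 0.405 + 0.20 × 0.603 = 0.357
- non-exposed: 0.25 × 0.169 + 0.35 × 0.231 + 0.25 × 0.405 + 0.15 × 0.603 = 0.315

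| Imbalance | Exposed mix | Non-exposed mix | 3-year risk | RR | 5-year risk | RR |
|---|---|---|---|---|---|---|
| None | 25/25/25/25 | 25/25/25/25 | 35.2% v 35.2% | 1.00 | 49.6% v 49.6% | 1.00 |
| Mild | 15/30/35/20 | 25/35/25/15 | 35.7% v 31.5% | 1.13 | 50.6% v 45.3% | 1.12 |
| Moderate | 10/25/35/30 | 35/35/20/10 | 39.7% v 28.1% | 1.41 | 55.4% v 41.1% | 1.35 |
| Strong | 5/15/40/40 | 50/30/15/5 | 44.7% v 24.5% | 1.83 | 61.3% v 36.5% | 1.68 |

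**Step 3. Do two strata help?** Within a stratum the risk is the weighted mean of its two groups. For the moderate case at 3 years:
- Low/Int-1: exposed (0.10 × 0.169 + 0.25 × 0.231)/0.35 = 0.213; non-exposed (0.35 × 0.169 + 0.35 × 0.231)/0.70 = 0.200; ratio 1.07.
- Int-2/High: exposed (0.35 × 0.405 + 0.30 × 0.603)/0.65 = 0.497; non-exposed (0.20 × 0.405 + 0.10 × 0.603)/0.30 = 0.471; ratio 1.05.

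The same calculation for the strong case gives ratios of 1.12 and 1.11, against 1.83 crude. Two strata remove most of the spurious gap in this model, but not all of it.

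**Step 4. Precision.** The Int-2/High stratum of the 150 non-exposed patients holds 150 × 0.40 = 60 (mild), 150 × 0.30 = 45 (moderate) or 150 × 0.20 = 30 (strong). For a 10% event rate the 95% half-width, 1.96 × √(0.1 × 0.9/n), is 7.6, 8.8 or 10.7 points. With four strata the High group alone would hold about 15 (moderate) or 8 (strong), with half-widths of about 15 and 21 points. That is why two strata are preferable.

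**The case against.** The best case for the plan is that it has been candid. Section 9.1.2 discloses the confounding and rules out comparison and testing. The summaries are to be made separately, and baseline characteristics are summarised by cohort, so an imbalance in risk group would be visible. The phase III studies are a second reference. Annex 2 explains that a checklist answer records whether the protocol addresses a question, so No shows that stratification is not included, not that it was considered and rejected. A statistical analysis plan, not available here, could add such tables.

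Much of this stands, and it rules out several stronger readings:

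- A reader might infer that the protocol plans a head-to-head display, or that its tables are bound to mislead. It plans neither a comparison nor a test, and how far crude figures mislead depends on a case mix that nobody yet knows.
- A reader might infer that any difference would reflect mainly patient selection. The illustration fixes the drug effect at zero, so it cannot show that. It also covers death only; the documents give no severity-specific rates for bleeding, infection or AML.
- A reader might extend the point to the primary safety analysis. ADRs and SAEs are collected for exposed patients, so there is no parallel non-exposed figure to be confounded.

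The illustration has a further limit. The medians come from an IPSS analysis of primary myelofibrosis, whereas the registry also enrols secondary disease and scores previously diagnosed patients by DIPSS.

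The remedy is partial too. The five IPSS factors in section 7 include constitutional symptoms but not spleen size, and massive splenomegaly is the manifestation that 9.1.2 names. Only routinely available data are recorded (9.3.1), so some categories will be missing. Risk category is not among the follow-up items in 9.3.3, so it cannot be relied on at later changes of exposure, although 11.2 expects patients to move between cohorts.

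None of this defends crude summaries by exposure as the only stated form of context when severity is the named reason that the cohorts differ.

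**Conclusion.** The point holds in a limited form. The protocol gives the non-exposed cohort an interpretive role, names severity as the confounder, lists severity measures at baseline, and states a presentation by exposure alone, which its own checklist confirms contains no stratified analysis. For deaths and events of special interest, crude summaries could mislead.

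Under exponential survival at the section 7 medians, no drug effect and assumed mixes, the crude death risk ratio runs from 1.13 to 1.83 at 3 years and from 1.12 to 1.68 at 5 years; with equal mixes it is 1.00. The direction rests on milder patients being given ruxolitinib less often. This is a worthwhile improvement to a descriptive plan. It is not an error in the primary analysis, and it is not evidence that stratification was deliberately refused.

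There is also an internal inconsistency that needs no assumption: section 9.9 and Annex 2 item 7.1 do not match the limitations and the confounder set out in 9.1.2.

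**What to change.** In 9.7.4 and 9.7.5, add summaries of deaths and events of special interest in each cohort by risk category at enrolment, low/intermediate-1 against intermediate-2/high. Label them descriptive, with no test. Show whether each category came from IPSS or DIPSS, and show missing values as their own row. Optionally repeat the tables by baseline spleen length and constitutional symptoms, which covers the manifestations that 9.1.2 names. Standardised rates are not needed; they could suggest a comparability that the protocol disclaims.

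State three limitations with the tables:
- the strata are small in about 150 non-exposed patients;
- confounding will remain within strata;
- baseline is the first observation at inclusion in the registry (9.3.2), and 9.2.2 admits patients who already had ruxolitinib through earlier supply programmes, so baseline severity may have been measured after treatment began.

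Reconcile Annex 2 items 7.1 and 10.4 and section 9.9 with 9.1.2. Item 10.5 can stay as it is if no adjustment is added.

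The cost is a few extra tables from data items already listed, with no change to data collection or recruitment. The drawback is imprecise cells: about 8 to 11 points either side of a 10% event rate in the higher-risk non-exposed stratum under the mixes above.

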9.2 Setting

9.2.1 Patient population

Adult patients with a diagnosis of primary or secondary Myelofibrosis

9.2.2 Inclusion and exclusion criteria

Inclusion criteria

• Patients diagnosed with primary Myelofibrosis according to WHO criteria and secondary Myelofibrosis (Post- PV MF and Post –ET MF) according to IWG-MRT (International Working Group for Myelofibrosis Research and Treatment) criteria.

Exclusion criteria

- Patients not providing informed consent
- Patients participating in an investigational study involving ruxolitinib or another JAK inhibitor

Note: patients previously treated with ruxolitinib through the Individual Patient Supply Program (IPSP) or enrolled in the Expanded Access Study CINC424A2401 and switched to commercial drug supply are eligible.

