9.10 Other aspects

Not applicable.

10 **Protection of human subjects**

Compliance with Novartis and regulatory standards provides assurance that the rights, safety, and well-being of patients participating in non-interventional studies are protected (consistent with the principles that have their origin in the Declaration of Helsinki) and that the study data are credible and responsibly reported.

This study was designed and shall be implemented and reported in accordance with the Guidelines for Good Pharmacoepidemiology Practices (GPP) of the International Society for Pharmacoepidemiology (ISPE 2008), the STROBE (Strengthening the Reporting of Observational Studies in Epidemiology) guidelines (Vandenbroucke et al 2008), and with the ethical principles laid down in the Declaration of Helsinki.

This study is fulfilling the criteria of a 'European Network of Centres for Pharmacoepidemiology and Pharmacovigilance (ENCePP) study' and follows the 'ENCePP Code of Conduct' (European Medicines Agency 2010).

Informed consent procedures

Eligible patients may only be included in the study after providing written (witnessed, where required by law or regulation), IRB/IEC-approved informed consent, or, if incapable of doing so, after such consent has been provided by a legally acceptable representative of the patient. In cases where the patient's representative gives consent, the patient should be informed about the study to the extent possible given his/her understanding. If the patient is capable of doing so, he/she should indicate assent by personally signing and dating the written informed consent document or a separate assent form. Informed consent must be obtained before any data are collected. The process of obtaining informed consent should be documented in the patient source documents.

Novartis will provide to treating physicians or other involved medical professionals in a separate document a proposed informed consent form that complies with the Declaration of Helsinki principle and regulatory requirements and is considered appropriate for this study.

11 Management and reporting of adverse events/adverse reactions

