11.1 Events of special interest

For all patients enrolled in the non-interventional study data for events of special interest will be collected. Events of special interest will be prompted at each visit. For all events of special interest the following information will be collected, where applicable:

- 1. The severity grade (CTCAE Grade 1-4), event outcome
- 2. Start and end dates of the event, unless unresolved at final examination, or no further change of the condition can be expected
- 3. Diagnostic measures and results related to the event, e.g., histopathology, microbiological laboratory results
- 4. Use of anti-infective therapies, transfusions or other medications related to the management of the event

For patients exposed to ruxolitinib until 28 days after treatment discontinuation, all events of special interest that fulfill the criteria of a SAE will be reported.

Events of special interest are:

Bleeding events

Bleeding events include all hemorrhages of any severity grade (CTCAE 1-4, events with fatal outcome):

- Minor hemorrhages, such as bruising or epistaxis
- Major bleeding events, such as intracranial or intra-abdominal hemorrhages
- Unusual bleedings reported by patients (prolonged or more severe menorrhagia, prolonged bleeding after trauma)

Serious or opportunistic infections

Serious or opportunistic infections are defined as bacterial, viral, fungal or parasitic infections that fulfill one of the following criteria:

- Requires anti-infective treatment
- Leads to significant disability or hospitalization

Secondary malignancies

• Any malignancy diagnosed after inclusion of patients in the non-interventional study will be reported including diagnosis of or progression of MF to AML.

Deaths

• All deaths including cause of death will be reported. Deaths occurring in ruxolitinib exposed patients represent a SAE

11.2 Collection and reporting of Serious Adverse Events and Adverse drug Reactions for ruxolitinib exposed patients

Adverse Drug Reactions to ruxolitinib

For the purpose of this study, an Adverse Drug Reaction (ADR) is defined as a response to ruxolitinib treatment (medical condition, clinical sign, and symptom or laboratory value) which is noxious and unintended. Response in this context means that:

- A causal relationship between ruxolitinib treatment and the event is at least possible as determined by the reporter
- The event occurred after first exposure to ruxolitinib (treatment emergent)

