The definition includes worsening of a pre-existing symptom or medical condition.

As data from patients exposed to ruxolitinib as well as unexposed patients will be collected in the non-interventional study and transitions from one cohort to the other are expected, the time window for the collection of ADRs is defined as the first day of exposure to ruxolitinib until 28 days after discontinuation of ruxolitinib.

As much as possible, each ADR should be evaluated to determine:

- The severity grade (CTCAE Grade 1-4), the event outcome
- Confirmation of a reasonable possibility that adverse event is related to ruxolitinib treatment: (no, yes)
- Start and end dates, unless unresolved at final examination, or no further change of the condition can be expected
- Action taken with respect to ruxolitinib (none, dose adjusted, temporarily interrupted, permanently discontinued)
- Whether it is serious, as per SAE definition

Once an adverse reaction is detected, it should be followed until its resolution or until it is judged to be permanent, and assessment should be made at each visit of any changes in severity, the suspected relationship to study drug, the interventions required to treat it, and the outcome.

Disease progression should not be regarded or reported as an adverse reaction itself unless associated with a separate adverse reaction, or unless suspected to be related to treatment.

All ADR's will be collected in a dedicated section of the e-CRF and reported in final study report. Interim summaries will be provided to Health Authorities with PSURs.

The occurrence of ADRs and EoSIs should be sought by non-directive questioning of the patient at each visit during the study. ADRs and EoSIs also may be detected when they are volunteered by the patient during or between visits or through physical examination, laboratory test, or other assessments. All ADRs and EoSIs must be recorded on the safety data collection case report/case record form (CRF) with the information detailed above.

Serious adverse event reporting

An Adverse Event for the purposes of this protocol is defined as the appearance of (or worsening of any pre-existing) undesirable sign(s), symptom(s), or medical condition(s) that occur after patient's signed Informed Consent has been obtained.

An adverse event is categorized as serious (Serious Adverse Event, SAE) if any of the below conditions is fulfilled:

- fatal or life-threatening

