- results in persistent or significant disability/incapacity
- constitutes a congenital anomaly or a birth defect
- requires inpatient hospitalization or prolongation of existing hospitalization, unless hospitalization is for :
 - Routine treatment or monitoring of MF, not associated with any deterioration in condition
 - Social reasons and respite care in the absence of any deterioration in the patient's general condition
 - Elective or pre-planned treatment for a pre-existing condition that is unrelated to the indication under study and has not worsened since the start of the drug of interest
- is medically significant, in that it may jeopardize the subject and may require medical or surgical intervention to prevent one of the outcomes listed above.
- may require treatment on an emergency outpatient basis for an event not fulfilling any of the definitions of a SAE given above and not resulting in hospital admission
- transmission of infectious agent via medicinal product

Any SAE occurring after the patient has provided informed consent and until 28 days after the patient has permanently discontinued ruxolitinib must be reported to Novartis within 24 hours of learning of its occurrence. Serious adverse events occurring more than 28 days after ruxolitinib discontinuation need to be reported only if a relationship to ruxolitinib is suspected.

In addition, if an RMP exists for the drug of interest any events of special interest must be sent to Novartis DS&E within the same timelines as a serious adverse event in order to facilitate required follow-up.

Recurrent episodes, complications, or progression of the initial SAE must be reported as followup to the original episode, regardless of when the event occurs. This report must be submitted within 24 hours of the treating physician or other involved health care professional receiving the follow-up information. An SAE that is considered completely unrelated to a previously reported one should be reported separately as a new event.

Novartis	Confidential	Page 30
Non-Interventional Study Ame	nded Protocol v01 (Clean)	Study No. CINC424AIC01T

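### Patients already on ruxolitinib are summarised with new starters, while ADRs count from first exposure and SAEs from consent, so the pooled incidence mixes observation periods and is likely to understate early risks

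*Protocol*

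**What the plan says.** **Who enters.** The note in Protocol 9.2.2 admits "patients previously treated with ruxolitinib through the Individual Patient Supply Program (IPSP) or enrolled in the Expanded Access Study" after a switch to commercial supply. There is no cap on their number and no limit on how long they have been treated.

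**Baseline.** Under 9.3.2, baseline, unless otherwise stated, "is defined as the first observation at the time the patient is included in the registry". It is tied to registry entry, not to the start of ruxolitinib.

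**ADR window.** Section 11.2 says "the time window for the collection of ADRs is defined as the first day of exposure to ruxolitinib until 28 days after discontinuation". One of its conditions for an ADR is "The event occurred after first exposure to ruxolitinib (treatment emergent").

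**AE and SAE window.** The same section limits adverse events to those "that occur after patient's signed Informed Consent has been obtained". Expedited reporting covers "Any SAE occurring after the patient has provided informed consent and until 28 days after the patient has permanently discontinued ruxolitinib", and later SAEs only if a relationship to ruxolitinib is suspected.

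**Grouping.** The safety set in 9.7.1 takes every patient with at least one ruxolitinib dose and one post-baseline safety assessment. Section 9.7.4 summarises on-treatment ADRs and SAEs, with exposed and non-exposed patients as the only stated split. In Annex 2, the answer is No for the definition of exposure (5.1), stratified analyses (10.4) and discussion of selection bias (12.1.1). Section 9.1.2 discusses confounding between exposed and non-exposed patients but not prior exposure.

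**The concern.** A patient who comes from the supply programme or the expanded access study has already lived through part of the treatment course. Patients who died on drug before enrolment cannot appear in the registry, and those who stopped early appear only if they happen to enrol. This is left truncation, and it removes early events selectively.

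Two consequences follow for the primary summaries. First, ADR and SAE incidences for the same prevalent user refer to different periods, although 9.7.4 tabulates them together and 11.2 treats them as linked: each ADR is rated for seriousness by the SAE definition, and each related SAE is also to be recorded as an ADR. Second, the pooled figure averages new starters, who are seen through their early treatment, with prevalent users, who largely are not.

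This matters because 9.1.2 proposes to read the results against phase III experience, and 9.7.7 uses the COMFORT rates as the yardstick. Trial rates normally run from the start of treatment. A lower early rate in a mixed cohort could be taken as reassurance when it partly reflects who was under observation, and when.

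**Working it through.** **1. The windows side by side**

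| Situation (Protocol 11.2) | ADR count | SAE count |
|---|---|---|
| On drug before consent; related serious event before consent | inside | outside |
| On drug before consent; event after consent | inside | inside |
| First dose after consent; event after first dose | inside | inside |

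The conflict is confined to patients already on drug at consent. For later starters, the on-treatment restriction in 9.7.4 should remove SAEs that precede the first dose.

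**2. The plan's own figure**

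Section 9.7.7 gives a 95% probability of at least one case among 300 exposed patients when the true probability is 1%: 1 - 0.99^300 = 0.951. The figure is correct. It treats all 300 as fully at risk. For an event confined to early treatment, only new starters contribute, so the probability is 1 - 0.99^n, with n the number of new starters:

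| Assumed prevalent share | n | Probability of at least one case |
|---|---|---|
| 10% | 270 | 0.934 |
| 25% | 225 | 0.896 |
| 50% | 150 | 0.779 |

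**3. Effect on the pooled rate**

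All inputs here are assumptions except the 3 to 5 years of follow-up, which comes from 9.1.2. Let f be the share of prevalent users, all past their first 6 months on drug at enrolment. Let r be the hazard in the first 6 months of treatment relative to the later hazard, and T the years on study.

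- Prevalent users: average rate 1.
- New users: average rate A = (0.5r + T - 0.5)/T = 1 + 0.5(r - 1)/T.
- Pooled relative to new users: (1 - f) + f/A.

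For T = 1, A = 1.5 (r = 2) or 2 (r = 3). For T = 3, A = 1.167 or 1.333. For T = 5, A = 1.1 or 1.2. Pooled/new-user ratios:

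| f | T = 1, r = 2 | T = 1, r = 3 | T = 3, r = 2 | T = 3, r = 3 | T = 5, r = 2 | T = 5, r = 3 |
|---|---|---|---|---|---|---|
| 25% | 0.917 | 0.875 | 0.964 | 0.938 | 0.977 | 0.958 |
| 50% | 0.833 | 0.750 | 0.929 | 0.875 | 0.955 | 0.917 |
| 75% | 0.750 | 0.625 | 0.893 | 0.813 | 0.932 | 0.875 |

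The shortfall is therefore about 8-38% over the first year on study (1 - 0.917 to 1 - 0.625) and about 2-19% over 3 to 5 years (1 - 0.977 to 1 - 0.8125). The model assumes that pre-enrolment events are not counted. If some pre-enrolment ADRs are entered retrospectively, the ADR shortfall is smaller, but the ADR and SAE figures then diverge further.

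**The case against.** The strongest reply is that much of this is analysis detail. Separating new from prevalent users, delayed entry and another baseline for later starters are things a SAP commonly settles, and the SAP is not shown. Section 9.7.4 does not forbid further splits, and prior-treatment dates are collected where available (9.3.2 item 11). That is fair for the table split taken alone. It does not dispose of the two start points, which the protocol itself fixes, nor of events that were never collected.

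It can also be argued that 11.2 is merely ambiguous: ADRs are sought at visits during the study, and adverse events are defined from consent, so an ADR window starting at consent might be meant for prevalent users. That reading is possible, but the text says first exposure, twice. The ambiguity is itself a reason to reconcile it.

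Several stronger readings are tempting, but the documents do not support them:

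- **Consent forbids the ADR window.** Section 10 says "Informed consent must be obtained before any data are collected". This governs when data are gathered, not the dates of the events recorded; 9.3.2 itself asks for past history after consent.
- **Denominators are inflated by unobserved time.** The protocol plans no person-time rate. Section 9.7.3 summarises exposure duration without making it a denominator.
- **The ADR window causes the under-count.** Opening it at first exposure would, if anything, admit some early ADRs. The loss comes from who is missing at enrolment.
- **On-drug baseline values bias the safety results.** Baseline feeds descriptive tables only, and no change-from-baseline safety analysis is stated.
- **All incidence is biased downward.** For late or cumulative risks, such as secondary malignancy, the effect may be small or reversed.

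Finally, admitting established users suits a long-term safety objective. Their inclusion is not the fault.

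**Conclusion.** The point holds in limited form. Followed as written, the protocol gives ADRs and SAEs different starting points in patients already on ruxolitinib and provides no separation of these patients from new starters. The pooled incidence therefore mixes observation periods and is likely to understate risks concentrated early in treatment. That the two groups are pooled follows from the safety set and from the only grouping stated; the protocol does not use the word.

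The direction for early risks is well founded. The size is not known, because the documents give neither the share of prevalent users, nor their prior exposure, nor the shape of the hazard. The ranges above show what plausible inputs would do; they are not estimates of the bias in this study. For the long-term objective, the 3- to 5-year range is the more relevant one. The sample-size figure checked in 9.7.7 is arithmetically right. This is a worthwhile, low-cost correction, not a flaw that invalidates the study.

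**What to change.** 1. In 11.2, reconcile the windows so that ADRs and SAEs entering the incidence both start at the later of consent and first ruxolitinib dose. This concerns what is counted in the tables; expedited reporting duties need not change.
2. List ADRs dated before consent separately as history, outside the incidence.
3. In 9.7.4, report new users (first dose on or after enrolment) and prevalent users separately, and then pooled, using the dates from 9.3.2 item 11.
4. If person-time rates are calculated, treat prevalent users as delayed entry, with no time at risk before enrolment.

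The cost is a wording change and one more table split. The downside is less precision in the new-user stratum: with 150 new users, for example, the probability of seeing at least one case of a 1% event in that stratum is 0.779, against 0.951 for 300. Prior-treatment dates are recorded only where available, so some patients may have to be classified as of unknown prior exposure.
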